5.2 ASSESSMENT OF SAFETY

Safety will be assessed descriptively based on:

- Adverse events (including drug-related AEs and AEs leading to discontinuation)
- Adverse events of special interest (AESI)
- Serious adverse events (SAEs)
- Safety laboratory tests
- Physical examination
- Vital signs (blood pressure, pulse rate, body temperature)
- 12-lead ECG
- Immunogenicity (ADA)

5.2.1 Physical examination

A complete physical examination will be performed at the visits as specified in the [Flow Chart](#). It includes at a minimum general appearance, neck, lungs, cardiovascular system, abdomen, extremities, and skin.

A targeted physical examination will be performed at visits as specified in the [Flow Chart](#). This includes vital sign assessment as well as an evaluation of the organ systems associated with AE(s) symptoms or laboratory abnormalities.

The results must be included in the source documents available at the site.

5.2.2 Vital signs

Vital signs will be performed pre-dose as well as within 1 hour post dose (Refer to [Flow Chart](#)). Vital signs include systolic and diastolic blood pressure, pulse rate (electronically or by palpation count for 1 minute) and body temperature. Vital signs will be measured after the patients has been sitting comfortably (resting) for at least 5 minutes. The results must be included in the source documents available at the site.

5.2.3 Safety laboratory parameters

Safety laboratory parameters to be assessed are listed in [Table 5.2.3:1](#). For the sampling time points please see the [Flow Chart](#).

All analyses will be performed by a central laboratory, the respective reference ranges will be provided in the ISF.

Patients do not have to be fasted for the blood sampling for the safety laboratory.

Instructions regarding sample collection, sample handling/ processing and sample shipping are provided in the Laboratory Manual in the ISF.

The central laboratory will send reports to the investigator. It is the responsibility of the investigator to evaluate the laboratory reports. Clinically relevant abnormal findings as judged by the investigator will be reported as adverse events (refer to [Section 5.2.6](#)).

In case the criteria for hepatic injury are fulfilled, a number of additional measures will be performed (Refer to [Section 5.2.6.1.4](#)) and the DILI Checklist provided in the ISF. The amount of blood taken from the patient concerned will be increased due to this additional sampling.

The central laboratory will transfer the results of the analysis to the sponsor.

Table 5.2.3:1 Safety laboratory tests

Category	Test Name
Haematology	Haematocrit Haemoglobin Red blood cell count (RBC) White blood cell count (WBC) Platelet count
Automatic WBC differential (relative and absolute)	Neutrophils, eosinophils, basophils, monocytes, lymphocytes
Manual differential WBC (if auto differential WBC is abnormal)	Neutrophils (stabs), eosinophils, basophils, monocytes, lymphocytes
Coagulation	Activated partial thromboplastin time (aPTT) Prothrombin time (Quick's test and International Normalized Ratio [INR]) Fibrinogen
Enzymes	Aspartate transaminase (AST) Alanine transaminase (ALT) Alkaline phosphatase (AP) Gamma-glutamyl transferase (GGT) Creatine kinase (CK) CK-MB, only if CK is elevated Lactate dehydrogenase (LDH)
Substrates	C-Reactive Protein (CRP) Serum albumin Creatinine Total bilirubin or Direct bilirubin Bilirubin Indirect (if total is elevated) Total protein Total cholesterol Triglycerides Plasma glucose BUN (blood urea nitrogen) Troponin (Reflex, in case of elevated CK) LDL-Cholesterol (if total cholesterol is elevated) HDL-Cholesterol (if total cholesterol is elevated)
Electrolytes	Sodium Potassium Chloride Calcium

Category	Test name
Urinalysis (Stix)	Urine nitrite Urine protein Urine glucose Urine ketone Urobilinogen Urine bilirubin Urine erythrocytes Urine leukocytes Urine pH
Urine-Sediment (only if urine analysis abnormal)	microscopic examination
Infection testing ¹	Hepatitis B Surface Antigen (qualitative) Hepatitis B core Antibody (qualitative) Hepatitis B Virus (HBV)-DNA (quantitative) ² QuantiFERON®-TB ³ Hepatitis C Antibodies (qualitative) HIV-1, and HIV-2 Antibody (qualitative)
Urine Pregnancy test ⁴ At the drug administration visits, the test will be performed prior to the administration of study drug	Human Chorionic Gonadotropin in urine
Serum Pregnancy test (only if urine pregnancy test is positive)	Human Serum Chorionic Gonadotropin

¹ Refer to exclusion criteria [Section 3.3.3](#) the [Flow Chart](#) and [Section 6.2.1](#) for details regarding infection testing).

² An HBV-DNA test should be conducted if Hepatitis B core Antibody is positive and Hepatitis B Surface Antigen is negative.

³ Patients with suspected false positive or indeterminate QuantiFERON TB result may be re-tested once. A PPD skin test may be performed locally in case of an indeterminate QuantiFERON TB result.

⁴ Urine pregnancy testing will be performed as indicated in the [Flow Chart](#).

NOTE: See [Section 4.2.1](#) and lab manual for lab procedures required for hypersensitivity and anaphylactic reactions.

5.2.4 Electrocardiogram

A central laboratory will not be used for ECG recording and evaluation.

The 12-lead ECGs must be administered by a qualified staff member and results will be recorded and reviewed prior to dosing as scheduled in the [Flow Chart](#). Where possible, ECG measurements should precede blood sampling to avoid impact of sampling on the ECG results. The investigator or a designee will evaluate whether the ECG is normal or abnormal and assess clinical relevance if abnormal. ECGs may be repeated for quality reasons and the repeated recording used for analysis.

Additional ECGs may be recorded for safety reasons. The dated and signed printouts of the ECG, will be regarded as source data and will be stored in the patient's medical file.

Clinically relevant abnormal findings will be reported either as baseline condition (if identified at Visit 1) or as adverse events and will be followed up and/or treated as medically appropriate.

5.2.5 Other safety parameters

All cases of malignancies that are detected during the trial will be reported as SAEs. Patients with a documented active or suspected malignancy (except for specific cancers) will be excluded from this trial per the exclusion criteria ([Section 3.3.3](#)).

5.2.6 Assessment of adverse events

5.2.6.1 Definitions of AEs

5.2.6.1.1 Adverse event

An AE is defined as any untoward medical occurrence in a patient or clinical investigation subject administered a medicinal product and which does not necessarily have to have a causal relationship with this treatment.

An AE can therefore be any unfavourable and unintended sign (including an abnormal laboratory finding), symptom, or disease temporally associated with the use of a medicinal product, whether or not considered related to the medicinal product.

The following should also be recorded as an AE in the CRF and BI SAE form (if applicable):

- Worsening of the underlying disease or of other pre-existing conditions.
- Changes in vital signs, ECG, physical examination and laboratory test results, if they are judged clinically relevant by the investigator.

If such abnormalities already exist prior to trial inclusion, they will be considered as baseline conditions and should be collected in the eCRF only.

5.2.6.1.2 Serious adverse event

A serious adverse event (SAE) is defined as any AE, which fulfils at least one of the following criteria:

- results in death,
- is life-threatening, which refers to an event in which the patient was at risk of death at the time of the event; it does not refer to an event that hypothetically might have caused death if more severe,
- requires inpatient hospitalisation or prolongation of existing hospitalisation
- results in persistent or significant disability or incapacity,
- is a congenital anomaly / birth defect,
- is deemed serious for any other reason if it is an important medical event when based on appropriate medical judgement which may jeopardise the patient and may require medical or surgical intervention to prevent one of the other outcomes listed in the above definitions. Examples of such events are intensive treatment in an emergency room or at home for allergic bronchospasm, blood dyscrasias or convulsions that do not result in hospitalisation or development of dependency or abuse.

For Japan only: the following events will be handled as “deemed serious for any other reason”. AEs which possibly lead to disability will be reported as SAEs.

5.2.6.1.3 AEs considered “Always Serious”

In accordance with the European Medicines Agency initiative on Important Medical Events, Boehringer Ingelheim has set up a list of further AEs, which by their nature, can always be considered to be “serious” even though they may not have met the criteria of an SAE as defined above.

The latest list of “Always Serious AEs” can be found in the electronic data capture (eDC) system. A copy of the latest list of “Always Serious AEs” will be provided upon request. These events should always be reported as SAEs as described above.

Cancers of new histology and exacerbations of existing cancer must be classified as a serious event regardless of the time since discontinuation of the drug and must be reported as per [Section 5.2.6.2](#), subsections “AE Collection” and “**AE reporting to sponsor and timelines**”.

5.2.6.1.4 Adverse events of special interest

The term adverse events of special interest (AESI) relates to any specific AE that has been identified at the project level as being of particular concern for prospective safety monitoring and safety assessment within this trial, e.g. the potential for AEs based on knowledge from other compounds in the same class. AESIs need to be reported to the sponsor’s Pharmacovigilance Department within the same timeframe that applies to SAEs, please see [Section 5.2.6.2.2](#). Refer also to [Section 1.4.2](#) and [Section 4.2.1](#)

The following are considered as AESIs:

Hepatic injury

A hepatic injury is defined by the following alterations of hepatic laboratory parameters:

- An elevation of AST (Aspartate Aminotransferase) and/or ALT (Alanine Aminotransferase) ≥ 3 fold ULN combined with an elevation of total bilirubin ≥ 2 fold ULN measured in the same blood draw sample, or
- Aminotransferase (ALT, and/or AST) elevations ≥ 10 fold ULN.

These lab findings constitute a hepatic injury alert and the patients showing these lab abnormalities need to be followed up according to the “DILI checklist” provided in the ISF.

In case of clinical symptoms of hepatic injury (icterus, unexplained encephalopathy, unexplained coagulopathy, right upper quadrant abdominal pain, etc.) without lab results (ALT, AST, total bilirubin) available, the investigator should make sure these parameters are analysed, if necessary in an unscheduled blood test. Should the results meet the criteria of hepatic injury alert, the procedures described in the DILI checklist should be followed.

Systemic hypersensitivity reactions including anaphylactic reaction

Any suspicion of severe systemic hypersensitivity reaction and of any potential cases of anaphylaxis should be defined and assessed using the criteria discussed in the statement paper from Sampson HA ([Appendix 10.1, R11-4890](#)).

Severe infections (according to RCTC grading in the ISF)

Opportunistic and mycobacterium tuberculosis infections

These include pneumocystis jirovecii, BK virus disease including PVAN, CMV, post-transplant lymphoproliferative disorder (EBV), progressive multifocal leucoencephalopathy, bartonellosis (disseminated only), blastomycosis, toxoplasmosis, coccidioidomycosis, histoplasmosis, aspergillosis (invasive only), candidiasis (invasive or pharyngeal), cryptococcosis, other invasive fungi (mucormycosis zygomycosis, rhizopus, mucor, lichtheimia), scedosporium/pseudallescheria boydii, fusarium), legionellosis, listeria monocytogenes (invasive only), tuberculosis, nocardiosis, non-tuberculous mycobacterium, salmonellosis (invasive only), HBV reactivation, herpes simplex (invasive only), herpes zoster, strongyloides (hyperinfection syndrome and disseminated forms only), paracoccidioides, penicillium marneffeii, sporothrix schenckii, cryptosporidium species (chronic only), microsporidiosis, leishmaniasis (visceral only), trypanosoma cruzi infection (Chagas' disease) (disseminated only), campylobacteriosis (invasive only), shigellosis (invasive only), vibriosis (invasive due to vibrio vulnificus), HCV progression [[R17-2617](#)].

5.2.6.1.5 Intensity (severity) of AEs

The intensity grading of AEs will be performed according to RCTC Version 2.0 developed by the [REDACTED] [R13-3515]. Refer to the ISF for intensity/severity classification.

Intensity options are:

- Grade 1 mild
- Grade 2 moderate
- Grade 3 severe
- Grade 4 life-threatening

5.2.6.1.6 Causal relationship of AEs

Medical judgement should be used to determine whether there is a reasonable possibility of a causal relationship between the adverse event and the given study treatment, considering all relevant factors, including pattern of reaction, temporal relationship, de-challenge or re-challenge, confounding factors such as concomitant medication, concomitant diseases and relevant history.

Arguments that may suggest that there is a reasonable possibility of a causal relationship could be:

- The event is consistent with the known pharmacology of the drug.
- The event is known to be caused by or attributed to the drug class.
- A plausible time to onset of the event relative to the time of drug exposure.
- Evidence that the event is reproducible when the drug is re-introduced.
- No medically sound alternative aetiologies that could explain the event (e.g. pre-existing or concomitant diseases, or co-medications).
- The event is typically drug-related and infrequent in the general population not exposed to drugs (e.g. Stevens-Johnson syndrome).
- An indication of dose-response (i.e. greater effect size if the dose is increased, smaller effect size if dose is reduced).

Arguments that may suggest that there is no reasonable possibility of a causal relationship could be:

- No plausible time to onset of the event relative to the time of drug exposure is evident (e.g. pre-treatment cases, diagnosis of cancer or chronic disease within days / weeks of drug administration; an allergic reaction weeks after discontinuation of the drug concerned).
- Continuation of the event despite the withdrawal of the medication, taking into account the pharmacological properties of the compound (e.g. after 5 half-lives). Of note, this criterion may not be applicable to events whose time course is prolonged despite removing the original trigger.

- Additional arguments amongst those stated before, like alternative explanation (e.g. situations where other drugs or underlying diseases appear to provide a more likely explanation for the observed event than the drug concerned).
- Disappearance of the event even though the trial drug treatment continues or remains unchanged.

5.2.6.2 Adverse event collection and reporting

5.2.6.2.1 AE Collection

The investigator shall maintain and keep detailed records of all AEs in the patient files.

The following must be collected and documented on the appropriate CRF(s) by the investigator:

- From signing the informed consent onwards until the individual patient's end of trial: all AEs (serious and non-serious) and all AESIs.
- After the individual patient's end of trial: the investigator does not need to actively monitor the patient for new AEs but should only report any occurrence of cancer and trial treatment related SAEs and trial treatment related AESIs of which the investigator may become aware of by any means of communication, e.g. phone call. Those AEs should be reported on the BI SAE form but not on the CRF.

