2. V1 of this extension trial should be preferably performed during the EOS of the preceding BI 655130 parent trial. When the visits are performed on the same day duplicate procedures across studies are performed once during the EOS/V1. If these visits are not performed on the same day then all V1 procedures need to be performed at that visit. The only exception is Infection Testing which does not have to be repeated if performed at EOS of the parent trial and there is a <12 week gap from EOS of parent trial to V1 of this trial. Refer also to [Section 6.2.1](#)
3. After the individual patient's end of the trial the investigator should report only any cancers of new histology and exacerbations of existing cancer, study treatment related SAEs and study treatment related AESIs of which the investigator may become aware of and only via the BI SAE form. Refer to [Section 5.2.6.2.1](#).
4. All patients who receive at least one dose in the trial, including those who discontinue treatment prematurely, should complete the EOT visit as soon as possible and complete the EOS visit 16 weeks after the date of last trial drug administration.
5. Where possible, electrocardiogram (ECG) measurements should precede blood sampling and drug administration. Refer to [Section 5.2.4](#)
6. Body Surface Area (BSA) will be calculated from Part A of the SCORAD. All assessments must be done prior to trial drug administration. The questionnaires completed by patients should be done first before the investigator assessments. Refer to [Section 6.2](#)
7. Only applicable for women of childbearing potential. Urine pregnancy tests will be performed at all visits indicated in the [Flow Chart](#). Urine pregnancy testing should be done prior to administration of study drug. Study drug should only be administered in case of a negative test result. In case of a positive urine pregnancy test, a serum pregnancy test will be performed at the central laboratory.
8. Complete Physical Examination (PE) includes general appearance as well as evaluation of all organ systems.
9. Targeted physical examination includes evaluation of organ systems associated with AE(s) symptoms or laboratory abnormalities.
10. Vital signs will be assessed pre dose as well as within 1 hour post dose.
11. Safety laboratory tests include clinical chemistry, haematology, coagulation, and urinalysis, and will be performed centrally. Where possible, safety laboratory tests are to be drawn prior to dosing.

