1.2.1.1 Residual Effect Period

The Residual Effect Period (REP) of BI 655130 is 16 weeks. This is the period after the last dose with measurable drug levels and/or pharmacodynamic effects still likely to be present.

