3. DESCRIPTION OF DESIGN AND TRIAL POPULATION

3.1 OVERALL TRIAL DESIGN AND PLAN

This is a multi-centre, multi-national open label extension clinical trial. It is anticipated that approximately 40 patients with AD will complete the parent clinical trial 1368-0032 as planned and be eligible for enrolment in this extension trial. Patients who withdrew treatment prematurely in 1368-0032 will not be eligible for this extension trial.

[figure not shown]
The purpose of the trial is to offer to all patients who completed the clinical trial 1368-0032 as planned, the option to continue to receive BI 655130 treatment if they have responded to treatment and meet all criteria for study entry.

Response to treatment is defined as a 50% or more decrease in EASI in the parent trial. Refer to [Section 3.3.1](#) and [Section 3.3.2](#).

After signing informed consent, and if all eligibility criteria are met, patients will receive the first dose of BI 655130 for this extension trial. All patients will be assigned to receive active treatment, administered subcutaneously (SC).

All patients will return 16 weeks post the last treatment for an End of Study (EOS) visit. The trial is estimated to last approximately 4 years. The trial will end when all patients discontinue treatment, have another means to obtain treatment with BI 655130 or if the development of the drug is terminated. Individual treatment will be stopped if a reason for withdrawal is met.

Figure 3.1:1 Trial Design

V1 is eligibility and first SC injection
 V1 should be preferably combined with EOS of trial 1368-0032.
 Maximum gap for enrolling is 12 weeks from parent 1368-0032

V = Study Visit
 W = Week (study weeks)
 EOT = End-of-Treatment
 EOS = End-of-Study

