6.2.3 End of Treatment and Trial Completion

For all treated patients termination of trial medication and trial completion must be recorded on the corresponding eCRF.

For the comprehensive list of the trial procedures required at the EOT and the EOS visits please refer to [Flow Chart](#).

The EOS visit must be performed 16 weeks after the date of last drug administration.

Early Treatment and Trial Discontinuation:

If trial treatment is discontinued prematurely prior to the planned [Flow Chart](#) EOT visit, every effort should be made to have the patient return and undergo the procedures for the EOT visit as well as the EOS visit 16 weeks after the last study drug administration as outlined in the [Flow Chart](#).

Patients who are unable to physically return to the study site for the EOT and EOS visits should be contacted by the site by phone to collect information pertaining to adverse events and changes to concomitant therapy.

Trial Completion:

Trial completion is defined as a patient having reached the EOS visit within the specified window per protocol.

Treatment Completion:

Treatment completion is defined as a patient completing Visit 52 which is the EOT visit after receiving approximately 4 years of treatment

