7.2.5 Safety analyses

Adverse events will be coded using the Medical Dictionary for Drug Regulatory Activities (MedDRA). Standard BI summary tables and listings will be produced. All adverse events with an onset between start of treatment and end of the REP, a period of 16 weeks after the last dose of trial medication, will be assigned to the on-treatment period for evaluation.

All treated patients will be included in the safety analysis. In general, safety analyses will be descriptive in nature and will be based on BI standards. No hypothesis testing is planned.

Statistical analysis and reporting of adverse events will concentrate on treatment-emergent adverse events, i.e. all adverse events occurring between start of treatment and end of the REP. Adverse events that start before first drug intake and deteriorate under treatment will also be considered as 'treatment-emergent'.

Frequency, severity, and causal relationship of adverse events will be tabulated by system organ class and preferred term after coding according to the Medical Dictionary for Drug Regulatory Activities (MedDRA).

Laboratory data will be analysed both quantitatively as well as qualitatively. The latter will be done via comparison of laboratory data to their reference ranges. Values outside the reference range as well as values defined as clinically relevant will be summarised. Groups (defined in [Section 7.2.1](#)) will be compared descriptively with regard to distribution parameters as well as with regard to frequency and percentage of patients with abnormal values or clinically relevant abnormal values.

Vital signs, physical examinations, or other safety-relevant data observed at baseline, during the course of the trial and at the end-of-trial evaluation will be assessed with regard to possible changes compared to findings before start of treatment.

[REDACTED]

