All other safety, efficacy and biomarker measurements will be assigned to visits based on extended time windows around the planned visit dates, defined relative to the day of first trial treatment (which is scheduled for Visit V2). These extended time windows are defined in [Table 6.7: 1](#).

Table 6.7: 1 Time windows for assignment of efficacy, safety lab, vital signs, and biomarker measurements to visits for statistical analysis

Visit number / name	Visit label	Planned day	Time window (Days)				
			Window (per CTP)	Start (per CTP)	End (per CTP)	Start (extended)	End (extended)
V1	Day 1	Day 1	n/a	1 ^A	1	1 ^A	1
V2	Week 4	Day 29	+/- 14	15	43	2	43
V3	Week 8	Day 57	+/- 14	44	71	44	71
V4	Week 12	Day 85	+/- 14	72	99	72	99
V5	Week 16	Day 113	+/- 14	100	127	100	127
V6	Week 20	Day 141	+/- 14	128	155	128	155
V7	Week 24	Day 169	+/- 14	156	183	156	183
V8	Week 28	Day 197	+/- 14	184	211	184	211
V9	Week 32	Day 225	+/- 14	212	239	212	239
V10	Week 36	Day 253	+/- 14	240	267	240	267
V11	Week 40	Day 281	+/- 14	268	295	268	295
V12	Week 44	Day 309	+/- 14	296	323	296	323
V13	Week 48	Day 337	+/- 14	324	351	324	351
V14	Week 52	Day 365	+/- 14	352	379	352	379
V15	Week 56	Day 393	+/- 14	380	407	380	407
V16	Week 60	Day 421	+/- 14	408	435	408	435
V17	Week 64	Day 449	+/- 14	436	463	436	463
V18	Week 68	Day 477	+/- 14	464	491	464	491
V19	Week 72	Day 505	+/- 14	492	519	492	519
V20	Week 76	Day 533	+/- 14	520	547	520	547
V21	Week 80	Day 561	+/- 14	548	575	548	575
V22	Week 84	Day 589	+/- 14	576	603	576	603
V23	Week 88	Day 617	+/- 14	604	631	604	631
V24	Week 92	Day 645	+/- 14	632	659	632	659
V25	Week 96	Day 673	+/- 14	660	687	660	687
V26	Week 100	Day 701	+/- 14	688	715	688	715
V27	Week 104	Day 729	+/- 14	716	743	716	743
...
V52	EoT	Day 1429	+/- 14	1415	1443	1415	1443
V53	EoS	Day 1541	+/- 14	1528	1555	1444	1555/EoT+ 16weeks

Days are counted relative to the day of first treatment, which is defined as Day 1.

^A Note that measurements made at Day 1 and assigned to the on-treatment period (because mistakenly made after start of injection of trial treatment) via assessment on date and time (i.e. safety laboratory) will not be assigned to Day 1. Such data will be listed only.

Repeated and unscheduled efficacy, safety and biomarker measurements will be handled similarly to scheduled measurements and will also be assigned to a time window depending upon the date of measurement.

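### EOS is planned for the very day the 16-week residual effect period ends, so an early EOS under a symmetric window would end full AE collection up to 13 days short (minor)

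*Protocol*

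**What the plan says.** **Length of the residual effect period.** "The Residual Effect Period (REP) of BI 655130 is 16 weeks" (protocol 1.2.1.1).

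**What counts as treatment-emergent.** Protocol 7.2.5 assigns to the on-treatment period all AEs "with an onset between start of treatment and end of the REP, a period of 16 weeks after the last dose of trial medication".

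**When EOS is due.** Three places in the protocol agree:
- Flow Chart footnote 4: treated patients, including those who stop early, should "complete the EOS visit 16 weeks after the date of last trial drug administration".
- Section 3.1: "All patients will return 16 weeks post the last treatment for an End of Study (EOS) visit".
- Section 6.2.3: "The EOS visit must be performed 16 weeks after the date of last drug administration". The same section defines trial completion as reaching EOS inside a window that the protocol specifies. The visible text does not say what that window is.

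**When full AE collection stops.** Under protocol 5.2.6.2.1, all AEs go on the CRF until the individual patient's end of trial. After that, "the investigator does not need to actively monitor the patient for new AEs". Only cancers and treatment-related SAEs or AESIs that come to the investigator's notice are reported, and "Those AEs should be reported on the BI SAE form but not on the CRF".

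**The EOS window in the SAP.** Table 6.7:1 has the row "V53 EoS Day 1541 +/- 14 1528 1555". The plus or minus 14, the start and the end stand in columns labelled as taken from the protocol.

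**The concern.** The period in which an AE counts as treatment-emergent and the period in which all AEs are collected are meant to end on the same day. With no slack between them, any EOS held before day 112 ends collection first. A non-serious AE, or an SAE or AESI judged unrelated, that starts between that visit and day 112 meets the protocol's definition of treatment-emergent, yet nobody is obliged to record it.

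The trial exists to gather long-term safety data in about 40 patients, so one patient in an AE row is about 1/40 = 2.5 percentage points. At stake are the last days of follow-up in the final AE tables.

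**Working it through.** **Inputs**
- Residual effect period: 16 weeks (protocol 1.2.1.1 and 7.2.5).
- Planned last dose for a completer: Visit 52, Day 1429 (protocol Flow Chart and 6.2.2).
- Planned EOS: Visit 53, Day 1541 (protocol Flow Chart).
- EoS window start: Day 1528 (SAP Table 6.7:1).
- Week 48 visit: Day 337.
- A patient's end of trial is read as EOS, in line with the completion definition in protocol 6.2.3.

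**Step 1: reproduce the plan's EOS day.** Residual effect period = 16 × 7 = 112 days. Its end = last dose + 112 = 1429 + 112 = Day 1541. This is the planned EOS day, so the planned gap is 0 days.

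**Step 2: gap with an early EOS.** Uncovered days = max(0, last dose + 112 − EOS day).

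| Last dose | Period ends | EOS | Uncovered days | Share of 112 |
|---|---|---|---|---|
| Day 1429 | Day 1541 | Day 1541 (planned) | 0 | 0% |
| Day 1429 | Day 1541 | Day 1528 (table start) | 13 | 13/112 = 11.6% |
| Day 1429 | Day 1541 | Day 1527 (literal minus 14) | 14 | 14/112 = 12.5% |

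**Step 3: when there is no gap.** With EOS no earlier than Day 1528, nothing is uncovered if the last dose was on or before Day 1528 − 112 = Day 1416.

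**Step 4: scale.** Against a completer's whole at-risk period (Days 1 to 1541), 13 days is 13/1541 = 0.84% and 14 days is 14/1541 = 0.91%. The window opens 1528 − 337 = 1191 days after the Week 48 visit.

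**Step 5: after the fix.** If EOS cannot fall before last dose + 112 days, the formula gives 0.

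No count of missed events can be given. The documents contain neither an AE rate for this period nor a distribution of EOS dates.

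**The case against.** The strongest reply is that the protocol already aligns the two periods. Section 6.2.3 says EOS must take place at 16 weeks, which read strictly rules out an early visit. The visible protocol text gives 14 days either way to treatment visits only. The EOT/EOS flow chart named in the table of contents is not visible and could already hold a one-sided window.

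SAP Table 6.7:1 is also imperfect evidence. It assigns measurements to visits for analysis and does not instruct sites, and SAP 6.7 says AE analysis does not use visit windows. Its start days are not a literal minus 14: EoS opens 13 days early, as V3 does (57 − 44 = 13), although no preceding window would overlap with Day 1527. The accompanying text also places first treatment at V2, whereas the table has it at V1.

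Much of this stands, and it makes the point conditional. It does not remove it. Section 6.2.3 itself refers to an EOS window, and the only visible statement of one is symmetric and labelled as the protocol's. That AE analysis ignores visits does not help, because the gap is in collection.

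The second reply is that SAP Table 6.1:1 ends the on-treatment period at EoT plus one day. If that rule governs the AE tables, the uncovered days fall outside them. This also stands as a condition. SAP 7.8.1 uses the treatment-emergent concept without redefining it, and the SAP says it builds on protocol Section 7, so the 112-day rule is the more natural reading.

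Three stronger readings may tempt a reader:
- **A gap of 27 days.** A last dose on Day 1443 ends the period on Day 1555, and 1555 − 1528 = 27. This requires counting EOS from Day 1, as protocol 6.1 does for visits in general. Section 6.2.3 counts EOS specifically from the last dose, so the documents do not support it.
- **Damage to the Week 48 primary endpoint.** For patients still on treatment at Week 48, the gap arises years later. For patients who stop early, no EOS window is visible, so no gap can be claimed.
- **Loss of serious safety information at large.** Cancers and related SAEs or AESIs remain reportable, and protocol 5.2.6.2.2 has AEs that persist beyond EOS followed up.

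**Conclusion.** The point holds as a minor, inexpensive improvement. The planned gap is 0 days. The largest gap for a completer dosed on schedule is 13 of 112 days, or 14 under a literal minus 14, which is under 1% of that patient's at-risk time. What may go uncollected is new non-serious AEs and unrelated SAEs or AESIs.

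It rests on four assumptions:
- the unseen EOT/EOS flow chart carries the symmetric window that the SAP shows;
- a patient's end of trial means EOS;
- the last dose is on Day 1429 (with the fixed window there is no gap if it is on or before Day 1416);
- protocol 7.2.5, not SAP Table 6.1:1, decides what enters the AE tables.

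If the first or the last fails, the end-of-trial AE tables are not affected by this gap. Confidence is medium for that reason.

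**What to change.** First check the EOS window in the EOT/EOS flow chart. If it is already one-sided, nothing needs to change in the protocol. If it is symmetric, do one of the following:

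1. Set the EOS window to 0/+14 days, counted from the actual last dose plus 112 days.
2. Keep the window, and when EOS fell before day 112, make a phone AE check at day 112 and enter the result on the CRF. Protocol 6.2.3 already uses phone contact for AEs when a patient cannot attend.

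Either reduces the uncovered time to 0. The first moves some EOS visits up to 14 days later. The second costs one call per early EOS. Both need a protocol amendment with the approvals described in protocol 8.1, so it is sensible to fold the change into the next amendment made for other reasons.
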